2.3 Risk/benefit assessment

2.3.1 Known potential risks

2.3.1.1 Toxic manifestations

Toxic manifestations related to the use of chloroquine are listed below:

- Cardiovascular alterations (hypotension, vasodilation, suppression of myocardial function, cardiac arrhythmias, cardiac arrest); rare electrocardiogram alterations, such as inversion of the T wave and enlargement of the QRS complex, AV block, cardiomyopathy;
- 2. Alterations of the central nervous system, the most common being: visual accommodation disorder, blurred vision, headache, fatigue, nervousness, anxiety, apathy. Rare alterations include irritability, agitation, aggression, confusion, personality change, depression and psychic stimulation, peripheral neuritis, neuromyopathy;
- 3. Digestive system, the most common being: gastrointestinal irritation, nausea, vomiting, stomatitis and rare fulminant liver failure;
- 4. Hematological: rare alterations include neutropenia, agranulocytosis, aplastic anemia, thrombocytopenia;
- 5. Renal, rare alterations include renal failure in patients with G6PD deficiency;
- 6. Dermatological: most common alterations include itching, dark blue coloration of the mouth, skin and nails, hair whitening, hair loss, skin rash.
- 7. Other common alterations include corneal opacity, acute attack of porphyria and psoriasis in susceptible people. Rare alterations include ototoxicity, muscle weakness. High daily doses (> 250 mg), resulting in cumulative doses of more than 1 g/kg of base chloroquine, can result in irreversible retinopathy and ototoxicity.

It is noteworthy that the use of the drug will be for a short time and, as such, it has rarely been associated with the risks described above, which are only ever seen in prolonged use of the medication.

2.3.1.2 Risks involving blood collection from biological samples

Blood collection may cause some discomfort in some people, dizziness, bleeding, bruising or swelling at the collection site. It can rarely cause fainting or infection.

2.3.2 Unknown risks

Other side effects not yet known at this time may happen during the study. All medications have a possible risk of an allergic reaction, which will be treated properly if or when it occurs.

2.3.3 Risks to privacy

Individuals will be asked to provide personal health information. All attempts will be made to keep this information confidential within the limits of the law. However, there is a possibility of loss of confidentiality. All study records will be kept in a closed file or in a locked room. Electronic files will be password protected. Only persons involved in conduct, supervision, monitoring or auditing will be allowed access to the information collected. No publication in this study will use information that could identify subjects by name.

2.3.4 Potential benefits

Information from this study can help treatment and management of hospitalized patients and will help future patients with COVID-19, reducing mortality caused by COVID-19 in hospitalized patients.

3. OBJECTIVES AND OUTCOMES

The general objective of the study is to evaluate the clinical efficacy, safety of therapy and reduction of mortality in hospitalized adult patients with severe respiratory syndrome using two different dosages of chloroquine. Objectives and outcomes are shown in table 2.

 Table 2: Objectives and outcomes.

| Objectives | Outcomes | | | | | | |
|--|---|--|--|--|--|--|--|
| Primary | | | | | | | |
| To assess whether the therapeutic regimen of | Reduction of mortality by 50% | | | | | | |
| Group 1 reduces mortality by 50% in the study | | | | | | | |
| population compared to Group 2. | | | | | | | |
| Secondary | | | | | | | |
| - Assess mortality on days 7, 14 and 28 after | - Mortality on days 7 and 14 | | | | | | |
| hospitalization; | - Clinical status of the subject on days 14 | | | | | | |
| - Assess clinical improvement (use of | and 28 | | | | | | |
| supplemental oxygen, ICU stay, length of stay | -Daily clinical status during | | | | | | |
| in the ICU, length of hospital stay, need for OTI | hospitalization | | | | | | |
| and time on mechanical ventilation, radiological | - Need for and duration of supplementary | | | | | | |
| alterations and time taken to improve the | oxygen | | | | | | |
| radiological and resonance pattern); | - Need for and duration of mechanical | | | | | | |
| - Assess the percentage of SARS-CoV2 | ventilation | | | | | | |
| detection in OPS and blood samples on days 1, | - Length of hospitalization | | | | | | |
| 3, 5, 7, 14 and 28 in the study population; | - Data and cause of death (if applicable) | | | | | | |
| Quantify the SARS-CoV2 virus in | - Prevalence of grade 3 and 4 adverse | | | | | | |
| oropharyngeal swab, nasal swab, OPS and blood | events; | | | | | | |
| samples on days 1, 3, 5, 7, 14 and 28 in the study | - Prevalence of serious adverse events; | | | | | | |
| population; | - Leukogram, hemoglobin, platelets, | | | | | | |
| - Alterations in white cell count, hemoglobin, | creatinine, CK, glucose, total bilirubin, | | | | | | |
| platelets, creatinine, glucose, total bilirubin, | ALT and AST on days 1, 3, 5, 7 (while | | | | | | |
| ALT and AST over time. | hospitalized); and on days 14 and 28 (if | | | | | | |
| - Cumulative incidence of serious adverse | patient is able to return to the clinic or is | | | | | | |
| events (SAEs); | still hospitalized); | | | | | | |
| - Cumulative incidence of grade 3 and 4 adverse | - Negative presence of the virus in | | | | | | |
| events (AEs); | respiratory secretion; | | | | | | |
| - Discontinuation or temporary suspension of | - Viremia by RT-PCR; | | | | | | |
| treatment (for any reason); | - Verification of anatomical-pathological | | | | | | |
| | alterations in cases that evolved to death. | | | | | | |

- In case of mortality, describe organic alterations based on a complete or minimally invasive autopsy.

4. STUDY DESIGN

4.1 General design of the project

This is a double-blind, randomized, placebo-controlled clinical trial. A total of 440 individuals, aged 18 years or older, diagnosed with severe respiratory disease, without contraindications to CQ, hospitalized in the HPSDRAA, with suspected SARS-CoV2, will be randomized into two treatment groups, in the ratio of 1:1, with group 1 receiving CQ 600mg twice a day for 10 days or group 2 receiving CQ 450mg twice a day on the first day and 450mg once a day the following 4 days. In order to blind study team and participants, placebo tablets will be used to standardize group 2 treatment for 10 days as group 1. Both groups will receive drugs via oral administration or nasogastric tube in case of orotracheal intubation. Chloroquine and placebo will be donated by Farmanguinhos on an emergency basis. Clinical and laboratory data during hospitalization will be used to assess the efficacy and safety outcomes. Blood samples and oropharyngeal swabs (OPS) will be obtained on days 1, 3, 5, 7, 14 and 28 (while hospitalized).

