1.6 Exclusion criteria

(Does not apply).

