1.12 Table 1: Schedule for evaluation throughout the study

| Description of the procedures according | D0* | D1∞ | D2 | D3 | D4 | D5 | D6 | D7 | D8 | D9 | D10 | D11 | Dx | D14# | D28# |
|--|-----|-----|-----|-----|-----|-----|-----|-----|-----|-----|-----|-----|-----|------|------|
| to the protocol $^{\mu}$ | D0 | Di | D2 | D3 | | | 20 | 2, | | | DIO | | | | D20 |
| Application of ICF ^t | X | | | | | | | | | | | | | | |
| Review of eligibility criteria ^a | X | | | | | | | | | | | | | | |
| Randomization ^b | X | | | | | | | | | | | | | | |
| Demography, medical history, including comorbidities (HAS, DM, dG6PD) and coinfections (HIV, TB, hepatitis) ^c | X | | | | | | | | | | | | | | |
| Physical exam ^d | X | | | | | | | | | | | | | | |
| Clinical evaluation ^e | X | X | X | X | X | X | X | X | X | X | X | Х | X | X | X |
| Evaluation of concomitant medication ^f | X | X | X | X | X | X | X | X | X | X | X | X | X | X | X |
| 12-lead ECG ^g | X | X | X | X | X | X | X | X | Х | X | X | X | X | X | X |
| Blood sample collection for hematology and biochemistry ^h | Х | (x) | (x) |
| Blood sample collection for virology and storage ⁱ | Х | Х | | X | | Х | | X | | | | Х | X | Х | Х |
| Oropharyngeal Swab and Nasal Swab | Х | X | | X | | X | | X | | X | | Х | X | X | X |
| Record of adverse events (serious and non-serious) ^j | X | X | X | X | Х | Х | Х | X | X | X | X | X | X | X | Х |
| Assessment of the primary outcome ^k | | | | | | | | X | | | | | | X | X |
| Record of secondary outcomes ¹ | | X | X | X | X | X | X | X | X | X | X | X | X | X | Х |

Version_2.0_23march2020

| Respiratory evaluation ^m | (x) |
|--------------------------------------|-----|-----|-----|-----|-----|-----|-----|-----|-----|-----|-----|-----|-----|-----|-----|
| Radiological evaluation ⁿ | (x) |

- μ All data from the study procedures will be collected and entered into the RedCap system;
- * Screening and Randomization may occur on the same day. All procedures must be performed before the study intervention;
- ∞ Evaluations and collections should take place after 24 hours of administration of the investigational product;
- τ The Informed Consent Form will be obtained by the study nurse directly from the participant, or in case of no possibility of this occurring (example: loss of level of consciousness), from a family member or legal guardian.
- Dx Days of hospitalization after completion of treatment;

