- # Participant may be hospitalized or discharged. In the latter case, there will be no outpatient return visit and the main outcome will be assessed by telephone. Note: all procedures will be performed during the hospitalization period and will be interrupted if the participant is discharged;
- a Inclusion/exclusion criteria will be fully assessed at visit D1, prior to inclusion. The diagnosis of SARS-CoV2 will occur a posteriori.
- b Randomization will take place in blocks of 4 with 110 participants each. There will be interim reviews when 25%, 50% and 75% of participants are included;
- c A complete medical history will be obtained prior to randomization to include assessments of cardiovascular, metabolic (for example, Type I or II diabetes mellitus), psychiatric (such as depression), renal (such as nephrolithiasis, nephropathy, renal failure) and bone disorders;
- d Physical examination will consist of evaluation of vital signs (heart rate, respiratory rate, systolic, diastolic and mean blood pressure, peripheral oxygen saturation) and signs and symptoms present;
- e Assessments to highlight any visual and/or mental alterations resulting from chloroquine;
- f Avoid administration of other drugs known to prolong the QT interval (ie quinolones, macrolides, ondansetron), as well as various antiarrhythmic, antidepressant and antipsychotic drugs; Avoid administration of other drugs known to prolong the QT interval (ie quinolones, macrolides, ondansetron), as well as various antiarrhythmic, antidepressant and antipsychotic drugs;
- g A 12-lead ECG will be performed in a semi-supine position after resting for at least 5 minutes. The intention is to exclude the development of prolongation in the QT interval or bradycardia;
- h Blood samples will be collected to assess the COVID-19 infection and perform laboratory tests requested by the doctor. In the case of Manaus, the evaluation of the infection by COVID-19 will take place at LACEN-FVS and the others will take place at the Delphina Rinaldi Abdel Aziz Hospital and A & E. In Niterói-RJ all tests will be performed at the hospital. In Mato Grosso do Sul, the evaluation of infection by COVID-19 will take place at LACEN-MS and any others will take place at participating hospitals;

Version 2.0 23march2020

- i Blood samples will be collected for storage in a biorepository for further evaluation of the immune response profile;
- j Evaluated according to the DAIDS table for clinical and laboratory events;

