5.3 Exclusion of specific populations

Children and adolescents will be excluded.

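### Section 4.1 bars patients with contraindications to chloroquine from randomisation, but no eligibility list carries or defines that bar, and the synopsis exclusion list says exclusions do not apply

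*Protocol*

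**What the plan says.** Section 4.1 gives the population to be randomised as adults "aged 18 years or older, diagnosed with severe respiratory disease, without contraindications to CQ". The eligibility lists stand elsewhere:

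- Section 1.6 Exclusion criteria (synopsis) reads, in full, "Does not apply".
- Section 5.3 reads, in full, "Children and adolescents will be excluded".
- Sections 1.6 Inclusion criteria and 5.2 require age 18 or over, hospitalisation and at least one of four severity signs. Section 5.2 adds clinical suspicion of COVID-19. Neither mentions contraindications.

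The schedule in section 1.12 tells staff which text to apply. Note a says "Inclusion/exclusion criteria will be fully assessed at visit D1, prior to inclusion", and it adds no criterion of its own. Note c says "A complete medical history will be obtained prior to randomization". The asterisked note, on screening and randomisation, says "All procedures must be performed before the study intervention". A 12-lead ECG is marked at D0. Note f, on concomitant drugs, begins "Avoid administration of other drugs known to prolong the QT interval".

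**The concern.** The protocol gives two different answers to one question: may an adult with a contraindication to chloroquine be randomised? Section 4.1 says no. The listed criteria, applied as written, say yes. The synopsis entry is more than an omission, because it states that there are no exclusion criteria.

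The stake is safety at entry. Section 2.3.1.1 lists arrhythmia, cardiac arrest and AV block among the toxic manifestations of chloroquine. Section 2.2 describes an outside recommendation for chloroquine that applied only in the absence of contraindications. That condition reached section 4.1 but not the lists. With five participating hospitals and no definition, sites could decide the same case differently.

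**Working it through.** No figure in the protocol is in dispute, so the check is a comparison of texts.

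| Place | Bars a contraindicated adult? |
|---|---|
| 4.1 General design | Yes, undefined |
| 1.6 Inclusion criteria | No |
| 1.6 Exclusion criteria | No; says exclusions do not apply |
| 5.2 Inclusion criteria | No |
| 5.3 Exclusion of specific populations | No; minors only |

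Count: 0 + 0 + 0 + 0 = 0 of 4 lists carry the bar. The parallel design paragraph in the synopsis (1.2) also omits it.

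**Test case.** Take a hospitalised adult with suspected COVID-19, a respiratory rate above 24 and a contraindication to chloroquine.

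1. Both inclusion lists are met: age, hospitalisation, one severity sign and, for 5.2, clinical suspicion.
2. The 1.6 exclusion entry removes nobody.
3. Section 5.3 does not apply to an adult.
4. The review under note a therefore finds the patient eligible.
5. Section 4.1 says that this patient is not among those to be randomised.

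Steps 4 and 5 cannot both stand.

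**Does another step act as the bar?**

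- Medical history (note c) is taken before randomisation, but no finding is said to make a patient ineligible.
- The D0 ECG must precede the intervention. It is not stated to precede randomisation, and no baseline threshold is given.
- The prescription and pharmacist step (6.6) comes after inclusion.
- Note f is advice on other drugs, not an entry rule.
- Stopping study drug (8.1.4), the two-weekly AE/SAE review (1.11.2) and DSMB unmasking after SAEs (section 7) all act after inclusion.

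These steps lower the risk, but none is an entry criterion.

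**Effect on the statistics.** Eligibility is settled before allocation and applies equally to both arms. The sample-size inputs (20% lethality, 50% reduction, 80% power, 5% alpha) do not refer to contraindications. The comparison of doses and its error rates are not altered.

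**The case against.** The strongest reply is that section 4.1 is itself protocol text, so randomising a contraindicated patient would already depart from the protocol. That stands. A reader might infer that the trial has no written bar at all, and that would be wrong. The bar is written, but in the design narrative rather than in the criteria that note a sends staff to, and it is undefined.

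A second reply is that the intent of 4.1 is not beyond doubt. The near-identical sentence in 1.2 omits the phrase. The 4.1 sentence also names a single hospital, while sections 1.9 and 5.5.1 together give five, so it is out of step elsewhere too. This also stands. It means that deleting the phrase is a possible repair, but it does not remove the contradiction.

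Third, it is fair to say that inclusion lists need not carry an exclusion and that 5.3 concerns special populations. The direct conflict is therefore between 4.1 and the synopsis exclusion entry. The other lists matter because they do not supply the bar either.

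Three stronger readings are tempting, and the documents do not support them:

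- *The dose gap measures the problem.* Group 1 is assigned 600 mg × 2 × 10 = 12,000 mg and Group 2 450 mg × 2 + 450 mg × 4 = 2,700 mg, a ratio of 4.4. These figures describe the design for every participant and do not size the inconsistency.
- *G6PD deficiency or a long baseline QT should have been exclusions.* The schedule records medical history "including comorbidities (HAS, DM, dG6PD" and coinfections, and section 2.3.1.1 mentions rare renal failure in G6PD deficiency. Nowhere is that deficiency called a contraindication, and no ECG limit is given.
- *Contraindicated patients will be enrolled in number.* Clinicians may well screen them out, and the documents give no frequency.

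**Conclusion.** The inconsistency holds. The bar in 4.1 is absent from all four eligibility lists, is defined nowhere, and is contradicted outright by the synopsis exclusion entry. A contraindicated patient could be judged eligible by staff who follow the listed criteria. This should be fixed as a matter of entry safety.

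The conclusion assumes that staff work from the listed criteria, as note a directs, and not from the design narrative. How many patients are affected cannot be estimated. The point gives no ground for doubting the randomised comparison, alpha, power or the target of 440.

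**What to change.** Replace the entry in 1.6 Exclusion criteria with *known contraindication to chloroquine* and add the same item to 5.3. The clinical team should set the list of contraindications. Staff should judge it before randomisation from the medical history already taken, and from the D0 ECG where available. No new test is needed.

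Deleting the phrase from 4.1 would also restore consistency, but it would remove the only entry safeguard that the protocol states. Adding the criterion is preferable.

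The same amendment can align three smaller mismatches:

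- The 18 to 80 age range in 1.2, against no upper limit in 1.6, 1.8, 4.1 and 5.2.
- Clinical suspicion of COVID-19, required in 5.2 but missing from the 1.6 inclusion list.
- The single hospital in 4.1, against the five listed sites.

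The cost is a few patients made ineligible, as 4.1 already states, and an amendment. Section 11.11 requires prior written CONEP approval, with an exception where immediate risk to patients must be ruled out.

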1.4.2 Secondary objectives

- 1. Assess mortality on days 7, 14 and 28 after hospitalization;
- 2. Evaluate indicators of clinical worsening (use of supplemental oxygen, ICU stay, length of stay in the ICU, length of hospital stay, need for intubation and time on mechanical ventilation, radiological alterations and time to improve the radiological and resonance pattern);
- 3. Assess the percentage of SARS-CoV2 detection in oropharyngeal swab, nasal and blood swab samples on days 1, 3, 5, 8, 11, 14 and 28, in the study population;

- 4. Quantify the virus that causes SARS-CoV2 in oropharyngeal swab, nasal and blood swab samples on days 1, 3, 5, 8, 11, 14 and 28, in the study population;
- 5. Cumulative incidence of adverse events (AEs);
- 6. Cumulative incidence of grade 3 and 4 serious adverse events (SAEs);
- 7. Discontinuation or temporary suspension of treatment (for any reason);
- 8. Alterations in white cell count, hemoglobin, platelets, creatinine, glucose, total bilirubin, ALT and AST over time;
- 9. In case of mortality, describe organic alterations via autopsy.

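### The virology and laboratory day lists omit the pre-dose D0 sample that Table 1 schedules, and D1 has three meanings, so the reference for change over time is not fixed

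*Protocol*

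**What the plan says.** Four places in the protocol list sampling days, and none of the lists includes D0.

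- 1.4.2 Secondary objectives, virology (percentage detected and quantity): "samples on days 1, 3, 5, 8, 11, 14 and 28, in the study population".
- Section 3, Table 2, virology: "samples on days 1, 3, 5, 7, 14 and 28 in the study" population.
- Section 3, Table 2, laboratory outcome: "ALT and AST on days 1, 3, 5, 7 (while" in hospital), then days 14 and 28.
- Section 4.1: "Blood samples and oropharyngeal swabs (OPS) will be obtained on days 1, 3, 5, 7, 14 and 28 (while hospitalized").

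The laboratory objective in 1.4.2 is worded "Alterations in white cell count, hemoglobin, platelets, creatinine, glucose, total bilirubin, ALT and AST over time". It names no reference value.

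Table 1 (section 1.12) has a separate D0 column, and its note requires D0 procedures to be done before study drug. Swabs, virology blood and hematology/biochemistry are all marked at D0. For D1 the note reads "Evaluations and collections should take place after 24 hours of administration of the investigational product". Footnote a to the same table says "Inclusion/exclusion criteria will be fully assessed at visit D1, prior to inclusion". The dosing tables in 1.10, 1.13 and 6.2 make D1 the first day of treatment.

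**The concern.** A description of laboratory changes or viral decline during treatment needs a value taken before treatment. The protocol schedules one but leaves it out of every passage that defines these outcomes. The label that opens each list, day 1, is not stable either. A site or analyst working from 4.1 or Table 2 alone cannot tell whether the first value is pre-dose or post-dose.

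Two things are at stake. First, safety is a stated aim, and patients enter severely ill; shock is one of the qualifying criteria in 5.2. Abnormal creatinine, transaminases or blood counts on arrival are therefore to be expected, and the D0 value is what separates them from abnormalities that arise on drug. Second, D0 is an obvious covariate for later viral load and laboratory values, and the lists give no prompt to use it.

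**Working it through.** **1. Day lists side by side**

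| Place | Days |
|---|---|
| 1.4.2, virology | 1, 3, 5, 8, 11, 14, 28 |
| Table 2, virology | 1, 3, 5, 7, 14, 28 |
| Table 2, laboratory | 1, 3, 5, 7, 14, 28 |
| 4.1, blood and swabs | 1, 3, 5, 7, 14, 28 |
| Table 1, virology blood | D0, 1, 3, 5, 7, 11, Dx, 14, 28 |
| Table 1, swabs | D0, 1, 3, 5, 7, 9, 11, Dx, 14, 28 |

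Dx stands for hospital days after treatment ends. D0 appears only in Table 1. The lists also disagree among themselves: 1.4.2 has days 8 and 11 where Table 2 and 4.1 have day 7, and Table 1 has no virology sample on D8. The Table 1 hematology/biochemistry row is damaged in the text available, so only its D0 mark is used here.

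**2. Meanings of D1**

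- Table 1 note: 24 hours after administration.
- Table 1, footnote a: before inclusion. The eligibility and randomization rows of the same table are marked at D0.
- Dosing tables: first treatment day.

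These cannot all describe one sampling time. The first is the only one that expressly times D1 collections.

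**3. Exposure at D1 on the Table 1 timing**

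The doses are those in 4.1 and 6.2. It is assumed that both first-day doses have been given by 24 hours.

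- Group 1: 2 × 600 = 1200 mg, out of 20 × 600 = 12,000 mg for the course (10%).
- Group 2: 2 × 450 = 900 mg, out of 2 × 450 + 4 × 450 = 2,700 mg (33%).

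On this reading the first listed value is post-dose, and exposure already differs between arms.

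**4. What D0 adjustment could add (illustration only)**

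Let ρ be the correlation between the D0 value and a later quantitative value. The protocol gives no figure, so 0.5 to 0.7 is assumed. Relative to an unadjusted comparison on the same day, residual variance is multiplied by 1 − ρ².

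- ρ = 0.5: 1 − 0.25 = 0.75, a 25% reduction; SE factor √0.75 = 0.87.
- ρ = 0.7: 1 − 0.49 = 0.51, a 49% reduction; SE factor √0.51 = 0.71.

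This applies to quantitative viral load and laboratory values. It does not carry over directly to percentage detected.

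**The case against.** A reader might infer that the trial measures change from an already treated value. The protocol does not say so. It defines no baseline and no change score, and it never names D1 as the reference. Section 10.1 lists descriptive statistics, chi-square and Fisher tests, and t or Mann-Whitney tests, none of them tied to a change from D1. The virology objectives are percentage and quantity on each listed day, and omitting D0 does not bias a randomized comparison on a single day.

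A reader might go on to put a size on that bias. With a constant daily difference in slope from the first dose, change from D1 would capture (3 − 1)/3 = 67% of the D0 to D3 difference and (5 − 1)/5 = 80% of the D0 to D5 difference. Both the slope and the change-from-D1 analysis would be the reader's own assumptions, so these are not losses in this trial.

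Nor is it right that admission abnormalities cannot be told apart from those arising on drug. If Table 1 is followed, the D0 value tells them apart.

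Finally, a baseline definition and covariate adjustment commonly sit in a statistical analysis plan, which is not at hand. That stands: the absence of an adjusted model is not an error, and adjustment is offered as an improvement. It does not dispose of the contradictory days and the three meanings of D1. Those are protocol instructions to sites, and an analysis plan cannot recover a pre-dose sample that a site working from 4.1 did not take.

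**Conclusion.** The point holds as an internal inconsistency. The virology and laboratory day lists omit the pre-dose sample that Table 1 schedules. D1 means three different things, and the lists conflict over days 7, 8 and 11. If the lists are applied literally with the Table 1 timing, the first listed value follows 1200 mg in Group 1 and 900 mg in Group 2 and could be taken as the reference for laboratory alterations over time. The protocol leaves that possible but does not prescribe it.

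Severity is minor. Only secondary outcomes are touched; the mortality outcome, sample size and interim boundaries do not change. The exposure figures assume that both first-day doses precede the D1 sample. The 25 to 49% variance reduction rests wholly on the assumed correlation.

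**What to change.** - In 1.4.2, Table 2 and 4.1, add D0 (pre-dose) to the day lists and name it as the reference for virology and laboratory outcomes.
- Report laboratory alterations as change, or new abnormality, from D0.
- Compare quantitative viral load and laboratory values on later days with adjustment for the D0 value, in place of the unadjusted t or Mann-Whitney tests in 10.1.
- Give D1 one meaning across Table 1, its footnote a and the day lists, stated so that it can be read together with the dosing tables. Footnote a should agree with the eligibility row, which is marked at D0.
- Settle on one set of later sampling days across 1.4.2, Table 1, Table 2 and 4.1, including day 7 against days 8 and 11, and the D9 and D11 collections in Table 1.

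The cost is wording and a short analysis specification. The D0 samples are already scheduled in Table 1, so naming them as the reference adds no sampling.
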